4.4 Study Endpoints

Outcomes measured at the prescription encounter level include whether the prescription is for a diabetes medication other than metformin, and whether the patient's most recent HbA1c value is within the Choosing Wisely HbA1c range guidelines for his/her age and morbidity category; these will be combined to classify the encounter as CW-compliant or CW-noncompliant. Outcomes measured at the physician level include these two measures, aggregated as a proportion of total prescription encounters within all eligible patients.

5 Study Enrollment and Withdrawal

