6.6 Unscheduled Visit

Not applicable.

7 Study Procedures/Evaluations

There are no study-specific procedures that patients will undergo. They will receive care as usual by their outpatient providers. In order to evaluate Choosing Wisely compliance status, the BE-EHR algorithm will capture information on demographics, diagnoses in the patient's problem list, prescription history, and relevant lab results (i.e. allergies and blood glucose (HbA1c)). The study team members will not collect this information directly; data will be collected in NYULH's EHR system, EPIC, and an EPIC Reporting analyst will extract the relevant parameters from the EHR into a report. The study team members only receive the ultimate determination from the algorithm that the patient is either CW-compliant or CW-noncompliant.

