10.1 Study Hypotheses

Patient in clinics receiving the BE-EHR module will have higher rates of CW compliance.

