10.2 Sample Size Determination

Our preliminary data indicate that approximately 30-40% of eligible patients have care that is CWcompliant. We wish to be able to detect an increase in the rate of CW-compliant care of ten percentage points or more. We conservatively estimate an ICC (intra-class correlation coefficient, a measure of the degree of additional correlation among providers within the same practice) of 0.05; with an average of four providers per practice site at 70 sites, this leads to a design effect of 1.15. The sample of 280 providers becomes an effective sample size of 244, providing approximately 87% power to detect a difference of ten percentage points between the study arms.

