10.3 Statistical Methods

We will begin all analyses with descriptive summary statistics and graphical displays of all variables. Primary analyses will utilize Poisson mixed-effects models for the provider-level CW compliance rate, with treatment group as the primary fixed effect of interest and practice as a random effect to accommodate clustering of providers within practices. We will assess whether negative binomial regression is warranted because of overdispersion. We will also explore non-parametric methods such as quantile regression and other rank-based approaches. Although randomization should obviate the need for any additional adjustment, we will explore whether adjustment for provider-level characteristics, such as demographics, panel size, or insurance mix, is necessary.

11 Source Documents and Access to Source Data/Documents

Source data is all information, original records of clinical findings, observations, or other activities in a study necessary for the reconstruction and evaluation of the study. Source data are contained in source documents. Examples of these original documents, and data records include: hospital records, clinical and office charts, laboratory notes, memoranda, subjects' diaries or evaluation checklists, pharmacy dispensing records, recorded data from automated instruments, copies or transcriptions certified after verification as being accurate and complete, microfiches, photographic negatives, microfilm or magnetic media, x-rays, subject files, and records kept at the pharmacy, at the laboratories, and at medicotechnical departments involved in the study.

The EPIC electronic health record is the primary data collection instrument for the study. Study-specific case report forms will not be used.

Access to study records will be limited to IRB-approved members of the study team. The investigator will permit study-related monitoring, audits, and inspections by the IRB/EC, the sponsor, government regulatory bodies, and University compliance and quality assurance groups of all study related documents (e.g., source documents, regulatory documents, data collection instruments, study data etc.). The investigator will ensure the capability for inspections of applicable study-related facilities (e.g., pharmacy, diagnostic laboratory, etc.).

12 Ethics/Protection of Human Subjects

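### Section 4.4 counts Choosing Wisely compliance per prescription encounter, but the data flow, hypothesis and planning baseline are per patient, and the primary model names no denominator

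*Combined protocol and SAP*

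**What the plan says.** - **4.4 Study Endpoints.** Two things are recorded at each prescription encounter: whether the drug is a diabetes medication other than metformin, and whether the latest HbA1c lies in the patient's range. Then "these will be combined to classify the encounter as CW-compliant or CW-noncompliant". At physician level the two measures are "aggregated as a proportion of total prescription encounters within all eligible patients". That sentence does not name the combined classification.
- **6 Study Schedule.** Any eligible patient with at least one encounter in the 18 months is included. No prescription is required.
- **7 Study Procedures/Evaluations.** The algorithm captures "diagnoses in the patient's problem list, prescription history, and relevant lab results", but "The study team members only receive the ultimate determination from the algorithm that the patient is either CW-compliant or CW-noncompliant".
- **10.1.** "Patient in clinics receiving the BE-EHR module will have higher rates of CW compliance".
- **10.2.** The baseline is that "approximately 30-40% of eligible patients have care that is CWcompliant". The sample is counted in providers: "The sample of 280 providers becomes an effective sample size of 244".
- **10.3.** "Primary analyses will utilize Poisson mixed-effects models for the provider-level CW compliance rate". Treatment is a fixed effect and practice a random effect. No numerator, denominator or offset is given, and 4.4 is not cited.

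**The concern.** The unit of analysis is not in doubt: 4.4, 10.2 and 10.3 all work at the level of the provider. What each provider's rate counts is unsettled. A Poisson model for a rate needs an exposure count, so the gap lies in the primary model itself. Two analysts could each follow the protocol faithfully and report different primary results.

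There is a second, conditional issue. The protocol does not define a prescription encounter. If it means an encounter with a diabetes prescription, the denominator arises after randomisation and the module may change it, because the module aims to reduce drugs other than metformin (Protocol Summary) and acts on refills (7.1). A patient whose non-metformin drug is stopped is a success for the module, yet could disappear from the rate. If the term means any prescription, such a patient usually stays in through another prescription and the issue shrinks.

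**Working it through.** **1. The sections side by side**

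| Section | What is counted |
|---|---|
| 4.4 | prescription encounters, over total prescription encounters |
| 6 | patients with at least one encounter of any kind |
| 7 | one determination per patient |
| 10.1 | patients |
| 10.2 | baseline in patients, sample in providers |
| 10.3 | provider rate, denominator not stated |

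**2. Can the Section 7 data give the 4.4 proportion?** The proportion needs, for each provider, the number of prescription encounters and how many of them were compliant. A single status per patient carries neither. It cannot represent a patient with both compliant and non-compliant encounters. In the other direction, a patient whom Section 6 includes but who has no prescription encounter contributes nothing under 4.4.

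**3. The plan's own figures (10.2).** Design effect: 1 + (4 − 1) × 0.05 = 1.15, as stated. Effective sample: 280 / 1.15 = 243.5, stated as 244. Neither uses a count of patients or encounters per provider.

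The 87% power does not follow from the stated inputs. On an assumed two-sided 5% test, treating each of 122 effective providers per arm as a single yes/no gives 34.7% to 37.2% over baselines of 40% down to 30%. The 87% is recovered if the provider rate is continuous with a standard error of 10 / (1.960 + 1.126) = 3.24 points, that is an SD of 3.24 × √(122/2) = 25.3 points. No SD is stated, and its value would depend on whether patients or encounters are counted.

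**4. The two units need not agree (hypothetical).** Let p be the share of patients who are compliant, and let non-compliant patients have k times as many prescription encounters as compliant ones. The encounter rate is p / (p + k(1 − p)). For a patient-level change from 35% to 45%:
- k = 1: 35% to 45%, 10 points.
- k = 2: 0.35/1.65 = 21.2% to 0.45/1.55 = 29.0%, 7.8 points.
- k = 0.5: 0.35/0.675 = 51.9% to 0.45/0.725 = 62.1%, 10.2 points.

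This needs no effect of the module on encounter counts. The documents give no value for k.

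**5. Patients leaving the count (hypothetical).** Assume one encounter per patient, b compliant per 100 at baseline, and 10 non-compliant patients who become compliant because a drug is stopped. A share s of those 10 no longer has a prescription encounter. The measured rate is (b + 10(1 − s)) / (100 − 10s). The true gain is 10 points.

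| b | s = 0 | s = 0.5 | s = 1 |
|---|---|---|---|
| 30 | 40.0% (+10) | 35/95 = 36.8% (+6.8) | 30/90 = 33.3% (+3.3) |
| 35 | 45.0% (+10) | 40/95 = 42.1% (+7.1) | 35/90 = 38.9% (+3.9) |
| 40 | 50.0% (+10) | 45/95 = 47.4% (+7.4) | 40/90 = 44.4% (+4.4) |

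The values of b span the stated 30-40%. The single encounter, the ten patients and s are assumptions.

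**The case against.** The best defence is that 4.4 is the endpoints section and does give an explicit physician-level denominator. The provider rate in 10.3 is then naturally the combined classification aggregated in the same way. Section 10.1 is a loosely worded hypothesis and 10.2 reports planning data; neither claims to define the endpoint. This stands in part: a reader who infers that the protocol has no definition at all goes too far. The defect is a conflict between sections. The defence does not remove it, because Section 7 does not deliver what 4.4 needs, 4.4 does not name the combined classification when it aggregates, and 10.3 does not point back to 4.4. An encounter proportion could be computed upstream in Epic, but the protocol does not describe that step.

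It is also fair that a prescription-encounter proportion is a legitimate endpoint for a module that nudges prescribers, and that a prescription has a natural prescriber while a patient may see several. A per-patient rate therefore needs an attribution rule, and the fix includes one.

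Two stronger inferences are tempting. One is that the encounter rate could rise with no change in any patient's status, if the module cut encounters among non-compliant patients. The documents give this little support: 4.2 describes the refill component as guideline information, 7.1 says the preference list does not restrict orders, and 12.3 says provider autonomy is unaffected. The other is to turn the 3.9 points into a loss of power. That would need the standard error back-solved in step 3 of the working, which comes from a power figure that the stated inputs do not yield and which itself depends on the unit in dispute.

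**Conclusion.** The conflict is in the current text and should be resolved before outcome data are examined, because choosing the unit afterwards would leave room for selective reporting. This part rests on no assumption: the data described in Section 7 cannot produce the 4.4 proportion, and some included patients have no outcome under 4.4.

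The concern about a denominator that responds to treatment is conditional on what a prescription encounter means. Neither its size nor its net direction can be computed from the documents. The fall from 10 points to 3.9 (3.3 to 4.4 over the stated baseline range) shows how the mechanism works under assumed inputs; it does not estimate what will happen in this trial. The 87% power should be called not reproducible from the stated inputs, and not wrong, since an unstated provider SD near 25 points would give it.

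**What to change.** - In 4.4, define the primary provider rate as CW-compliant eligible patients divided by all eligible patients with at least one encounter in the 18 months. Of the units in the text, this one matches the hypothesis, the data flow and the planning baseline.
- Classify each patient once, by a pre-stated timing rule common to both arms. The sponsor chooses the time point.
- Assign each patient to one provider and practice by a pre-stated rule that does not depend on arm, for example the first eligible encounter after randomisation. Primary care, geriatrics and endocrinology practices are all in scope, so a patient may be seen in more than one.
- State how patients with no diabetes prescription are scored, so that they are not dropped.
- Use that patient count as the denominator or offset in 10.3, and align 4.4, Section 7, 10.1, 10.2 and 10.3.
- Keep the prescription-encounter proportion as a secondary outcome, with the term defined and the proportion computed in the Epic report.
- Add a sensitivity analysis in patients already eligible at randomisation, because the count of patients seen also arises after randomisation.

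**Cost.** Protocol wording, a revised Epic report specification and an IRB amendment (12.2). No new data collection is needed if the rules draw on the prescription history and laboratory results that Section 7 already captures. The trial gives up several encounters per patient for one record. If a fixed late date is chosen, some patients will have died or left by then, which matters in a population aged 75 or older.

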4.2 Intervention

The BE-EHR module includes six components: 1) a tailored advisory for patients over 75 with diabetes, 2) medication refill protocol with information on Choosing Wisely guidelines, 3) pre-population of the medication preference list with metformin, 4) lab result protocol with information on Choosing Wisely

CONFIDENTIAL

guidelines, 5) peer comparisons regarding performance meeting guidelines, and 6) media campaign with information about Choosing Wisely guidelines. The set of nudges is referred to collectively as the BE-EHR module.

To tailor the intervention appropriately, we use a life expectancy algorithm to address different target patient populations with different CW guidelines. The life expectancy algorithm was built into the BE-EHR module to drive timing and content of module firings that incorporate both patient life expectancy (high, medium, low) and target glycemic index per the CW guideline. These categories are defined as follows:

1) healthy older adults with long life expectancy (>10 years): HbA1c target range of 7-7.5%;

2) those with moderate comorbidity and a moderate life expectancy (3-10 years): HbA1c target range of 7.5-8%;

3) those with multiple comorbidities and shorter life expectancy (\leq 3 years): HbA1c target range of 8-9%.

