7.1 Procedures/Evaluations

Practice sites will be randomized using variable block sizes of 4 and 6 to ensure balance, with an even randomization ratio that will result in half of the sites randomized to the BE-EHR module activation (BE-EHR) and half randomized to usual care (UC). Randomization will be stratified by practice size (<= 100 patients vs > 100 patients over 75 with diabetes) to ensure balance. See Section 4.3 for greater detail.

Eligible patients from the chosen practice sites will be identified electronically within EPIC using an algorithm developed by the study team. This algorithm reviews patient records for diabetes codes in the Problem List. Patients 75 and over with one of the included codes are eligible. The algorithm is outlined below as well as a description of each component of the interventional module:

- 1. Evaluation of Choosing Wisely compliance using a built-in algorithm. The life expectancy algorithm was built into the BE-EHR module to drive timing and content of module firings that incorporate both patient life expectancy (high, medium, low) and target glycemic index per the CW guideline. These categories are defined as follows:
 - 1) healthy older adults with long life expectancy (>10 years): HbA1c target range of 7-7.5%
 - 2) those with moderate comorbidity and a moderate life expectancy (3-10 years): HbA1c target range of 7.5-8%
 - those with multiple comorbidities and shorter life expectancy (≤3 years): HbA1c target range of 8-9%
- 2. Firings of various module components using internal EPIC reporting. Each of the six components is triggered when a participant who has lower than recommended glycemic control is encountered in the system.
 - 1) Tailored Advisory: The Tailored Advisory nudge activates in Epic for any patient who is not CW compliant. For each patient seen, clinicians can respond by clicking the "Agree with

recommendation. Action taken" button, or by selecting the "Clinically inappropriate. Please explain" option, with space for free text comments. A response is not required.

- 2) Refill Protocol: The Refill Protocol nudge activates in Epic any time a medication refill for either Metformin or a non-Metformin diabetes medication is generated for a patient over 75
- 3) Preference List: The Preference List nudge is a system level nudge at the pilot sites. Metformin is listed at the top of the page as the choice for "First-line Type 2 Diabetes," without restricting orders for non-Metformin medications.

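### Section 7 gives the study team only a compliant/non-compliant status, which cannot supply the plan's component and prescribing outcomes or show the direction of out-of-range HbA1c

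*Combined protocol and SAP*

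**What the plan says.** - **Section 4.4** defines two yes/no items for each prescription encounter: whether the drug prescribed is a diabetes drug other than metformin, and whether the patient's "most recent HbA1c value is within the Choosing Wisely HbA1c range guidelines". Of the two items it says "these will be combined to classify the encounter as CW-compliant or CW-noncompliant", with no operator, table or cross-reference. It adds: "Outcomes measured at the physician level include these two measures, aggregated as a proportion of total prescription encounters".
- **Section 4.2** gives each range a lower and an upper limit: "HbA1c target range of 7-7.5" per cent for the longest life expectancy, then 7.5–8% and 8–9%.
- **The Protocol Summary** names guideline compliance as the primary endpoint and prescribing patterns as the secondary one. It describes compliance as generally meaning looser HbA1c targets and less use of drugs other than metformin.
- **Section 7** says that the algorithm captures diagnoses, prescriptions and HbA1c, and that a reporting analyst extracts what is relevant. It closes by limiting the study team to the final status, worded per patient rather than per encounter.
- **Section 7.1** opens its list by saying that each of the six components is "triggered when a participant who has lower than recommended glycemic control is encountered in the system". The entries that follow read differently. "The Tailored Advisory nudge activates in Epic for any patient who is not CW compliant". The lab nudge follows a new HbA1c result in a non-compliant patient. The refill nudge fires "any time a medication refill for either Metformin or a non-Metformin diabetes medication is generated for a patient over 75". "The Preference List nudge is a system level nudge at the pilot sites". Peer comparison is a monthly e-mail, and the campaign entry names no patient trigger.
- **Section 10.2** plans on 30–40% compliance at present and a ten-point increase.

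**The concern.** The plan promises outcomes that need more data than Section 7 says the team will receive. A single status per patient or encounter does not reveal which drug class was prescribed or whether HbA1c was in range, yet both are to be reported per physician, and prescribing patterns are a named endpoint.

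Direction is a second problem. The module encourages less intensive control, so the natural follow-up to any compliance result is whether encounters moved from below range into range or past it. Neither the status nor an in-range/out-of-range item separates the two sides. A null or a positive result would be harder to interpret, and a rise in above-range values would not appear in the report.

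**Working it through.** The plan has no figure on this point to reproduce. The 30–40% comes from preliminary data that the documents do not show. The check sets the sections side by side.

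**Step 1: encounter types.** Drug class of the prescription (metformin, other) by HbA1c (below, in, above range) gives 2 × 3 = 6 types. Write their shares as m_b, m_i, m_a for metformin prescriptions and o_b, o_i, o_a for other drugs; they sum to 1. Drug class here describes the prescription, not the patient's whole regimen.

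**Step 2: two rules the text could bear.** Rule A joins the two items of Section 4.4: non-compliant if another drug is prescribed and HbA1c is not within range. Rule B follows the one-sided guideline quoted in Section 2.1.2: non-compliant if another drug is prescribed and HbA1c is below range.

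| Prescription, HbA1c | Rule A | Rule B |
|---|---|---|
| metformin, below | compliant | compliant |
| metformin, in | compliant | compliant |
| metformin, above | compliant | compliant |
| other, below | non-compliant | non-compliant |
| other, in | compliant | compliant |
| other, above | non-compliant | compliant |

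The rules differ in one type: other drug, above range.

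**Step 3: can the status supply the promised outcomes?**

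- The non-compliant share is o_b + o_a under A and o_b under B.
- The drug-class measure is o_b + o_i + o_a. Moving share from m_i to o_i changes it and leaves the status unchanged under both rules.
- The HbA1c measure is m_i + o_i. Moving share from m_b to m_i changes it and leaves the status unchanged under both rules.

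So neither component measure follows from the status, and neither do prescribing patterns.

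**Step 4: do the component measures restore direction?** Suppose the team had the status rate and both physician-level proportions. Six shares, less one for the sum and three for the known quantities, leaves 6 − 1 − 3 = 2 undetermined under either rule.

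Now move a share x from o_b to o_a:

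- Rule A: (o_b − x) + (o_a + x) = o_b + o_a, so the status does not change. The drug-class and HbA1c measures do not change either.
- Rule B: non-compliance falls by x and is counted as improvement. The HbA1c measure does not change, and nothing reported shows the rise above range.

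There is one exception. Under B, if both items arrived with the status for each encounter, an other-drug encounter that is out of range but compliant must be above range. The below/above split for metformin prescriptions would still be unknown.

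**Step 5: why the rule matters for the planning figure.** Compliance under B exceeds compliance under A by exactly o_a. The documents do not give o_a. Assuming 20–30% of encounters above range and 40–70% on another drug, independently, the gap runs from 0.20 × 0.40 = 0.08 to 0.30 × 0.70 = 0.21, that is 8 to 21 percentage points. These inputs are illustrative, not estimates, and they do not show which rule lies behind the 30–40%.

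**Step 6: the Section 7.1 lead-in against its list.**

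- Refill (any diabetes refill over 75), preference list (system level), peer comparison (monthly) and campaign (no patient trigger): the lead-in does not fit these four.
- Advisory and lab nudge (non-compliant status): the lead-in fits under B and does not fit under A, because A makes some above-range patients non-compliant.

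**The case against.** The closing sentence of Section 7 ends a paragraph about evaluating compliance, so it may describe that one variable only. The same paragraph has an analyst extracting relevant parameters, Section 12.3.3 has study team members generating Epic reports, and the HbA1c values stay in the record. The composite can test the hypothesis in Section 10.1. The below/in/above field and the extra rows are new reporting requests.

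Much of this stands. No data are lost, and the remedy is mainly wording. But the sentence says that the team gets only the status, and no section says that the component items will be delivered. Even if they were, the two-valued HbA1c item would not show direction.

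A reader might go further and infer that the primary compliance rate is left open, because a rule in which either item alone makes an encounter non-compliant could also be read into Section 4.4. The documents do not support that. The guideline in Section 2.1.2 concerns drugs other than metformin used to reach a low HbA1c, which joins the two conditions. Section 7.1 says that a built-in algorithm evaluates compliance, so the gap is an unprinted rule, not discretion left to whoever analyses the data.

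A reader might also infer that all six component descriptions contradict the lead-in. That is clear for four; for the advisory and the lab nudge it depends on how above-range values are classed.

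**Conclusion.** The point holds. Read as written, Section 7 cannot supply the two physician-level measures of Section 4.4 or the secondary prescribing endpoint, and the two-sided in-range item cannot separate below-range from above-range HbA1c. This rests on taking the binary-only sentence literally and on reading the within-range test as two-sided.

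The documents do not show that any offset will occur, and its size cannot be computed from them. The consequence is a gap in interpretability and in safety-relevant description, not an invalid primary test.

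The unprinted combining rule and the Section 7.1 lead-in are secondary wording points. The rule's open question is the single type of other drug with HbA1c above range. A specification may exist outside the protocol, but Section 4.4 cites none.

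**What to change.** **Main change**

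- Amend Section 7 so that the Epic extract includes, for each encounter, the drug class of the prescription (metformin or other) and the HbA1c position (below, in or above range).
- Beside the composite, report by arm the share of encounters below range on a non-metformin drug and the share above range.

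**Wording points**

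- State in Section 4.4 the combining rule already built into the algorithm, including how above-range values are classed, and check that the Epic flag matches it.
- Confirm in Section 10.2 that the 30–40% planning figure used that rule.
- Reconcile the Section 7.1 lead-in with the six component descriptions.

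The clinical leads decide the classification and the triggers; no view is taken here on which is right.

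**Cost:** one or two extract fields, two descriptive rows, a check of the flag and protocol wording. Any change to the triggers as built would depend on what the clinical leads decide and is not counted.
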